2.3. Benefit/Risk Assessment

2.3.1. Risk Assessment

Risks associated with LY3454738

No dose-limiting safety issues have been identified in clinical studies of participants receiving single or repeat doses of LY3454738. In a Phase 1 study comparing LY3454738 versus placebo in AD (Study FRCC), **CCI**

CCI
CCI

Based on these data and on other available clinical and nonclinical data, there are no anticipated risks that would require safety monitoring in this study beyond what is typical for clinical studies involving humanized mAbs.

The administration of therapeutic mAbs to humans can be associated with **CCI**

CCI

CCI**Risks and discomforts associated with study procedures**

Participants will use additive-free emollients during the study but will refrain from other topical AD treatments, with the exception of rescue medication as described in Section 6.9.1.

Participants accustomed to using TCS and other topical treatments may experience increased discomfort due to itching during the study.

Risk mitigations

The study entry criteria of the master IMMB protocol and of this ISA exclude potential participants who may be at greater risk of developing infections, **CCI** [REDACTED] **CCI** [REDACTED] or malignancies. Participants who may be at greater risk for adverse effects related to TCS withdrawal (Hajar et al. 2015) are also excluded.

To reduce the burden of untreated AD symptoms, qualifying participants are permitted to receive rescue medication during certain study periods (Sections 4.1 and 6.9.1).

All participants will have appropriate predose safety assessments, including symptom-directed physical assessments, clinical safety laboratory tests, suicidality/self-harm evaluations, vital signs, and evaluation of reported AEs, during the treatment period. The design includes posttreatment follow-up visits at which safety assessments are also conducted.

CCI

[REDACTED] Ongoing study-level monitoring of safety data will be performed, as described in Section 8.2 of the master IMMB protocol. Interim analyses of unblinded safety data will also be conducted, as described in Section 9.4 and Attachment 3, Section 10.3, of this ISA.

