4.1. Overall Design

This is a Phase 2, multicenter, randomized, double-blind, placebo-controlled, parallel-group, outpatient dose-ranging study to evaluate the efficacy and describe the safety of multiple LY3454738 induction and maintenance dosing regimens in adult participants with moderate-to-severe AD. The study population includes CCI

CCI participants, all with diagnosed AD which is moderate to severe as measured by EASI score ≥ 16 , vIGA-AD score ≥ 3 , and $\geq 10\%$ of BSA involvement at randomization.

Study periods

[figure not shown]
A schematic of the design of this ISA is presented CCI Assessments, sample collections, and study drug administrations occur at the visits shown in the SoA (Section 1.3).

Screening period and randomization to treatment within this ISA (Visit 0)

Screening for this ISA can begin up to CCI days before Study Day 1 (day of first dose). Informed consent for participation in this ISA must be obtained before any ISA-specific tests or procedures are performed. Screening activities for this ISA are listed in the SoA (Section 1.3) in the columns for CRF Visit 0 (V0).

Before a participant is randomized to a study intervention, the participant's eligibility according to the study entry criteria of both the master IMMB protocol (Section 5) and this FR01 ISA (Section 5) must be confirmed.

CCI

Induction regimen	Approximate total number of participants planned
LY3454738 CCI mg	96
LY3454738 CCI mg	68
LY3454738 CCI mg	28
Placebo	68

Blinded induction period

Randomized participants will begin the double-blind, placebo-controlled, 16-week induction period when the initial dose is administered on Study Day 1.

Topical rescue medication is permitted from Week 8 until Week 16 for participants who do not achieve an CCI response, as described in Section 6.9.1. Topical rescue medication started during the induction period should be stopped at, or before, Week 16.

Blinded maintenance period

The blinded CCI-week maintenance treatment period begins with the dose administered at Week 16. Participants having at least an CCI response at Week 16 will receive a maintenance dosing regimen, as listed here.

Week 16 responders who were originally randomized to this induction regimen...	Will receive this maintenance regimen:
LY3454738 CCI mg CCI	by rerandomization in CCI ratio: LY3454738 CCI mg CCI or placebo
LY3454738 CCI mg CCI	LY3454738 CCI mg CCI
LY3454738 CCI mg CCI placebo	LY3454738 CCI mg CCI Placebo CCI

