4.6.5.2. Vital Signs, Physical Findings, and Other Observations Related to Safety	21
4.6.5.3. Hepatic Safety	22
4.6.5.4. Infections	22
4.6.5.5. Malignancy	24
4.7. Other Analyses.....	24
4.7.1. Subgroup Analyses	24
4.8. Interim Analyses.....	24
CCI [REDACTED]	25
4.9. Changes to Protocol-Planned Analyses	25
5. Sample Size Determination	26
6. Supporting Documentation	27
6.1. Appendix 1: Demographic and Baseline Characteristics	27
6.2. Appendix 2: Definition of Efficacy Endpoints and Patient- Reported Health Outcomes.....	28
6.3. Appendix 3: Laboratory Analytes for Safety Analyses	31
7. References.....	32

Table of Contents

Table		Page
Table 1.1. SAP Version History Summary	4	
Table 3.1. The Minimum Analysis Sets for the ADMP.....	9	
Table 4.1. Baseline and Postbaseline Period Definitions for Overall and Induction Safety Analyses.....	14	
Table 4.2. Tables and Listings Related to Adverse Events.....	17	
Table 4.3. Tables and Figures for Clinical Laboratory Evaluations	20	
Table 4.4. Tables and Figures for Vital Signs and Physical Characteristics.....	21	
Table 4.5. Summary Tables and Figures Related to Hepatic Safety.....	22	
Table 4.6. Summary Tables, Figures, and Listings Related to Infection Safety	24	
Table 6.1. Demographic and Baseline Characteristic Variables.....	27	
Table 6.2. Derivation of Efficacy and Patient-Reported Health Outcomes	28	
Table 6.3. Laboratory Analytes.....	31	

Version History

This Statistical Analysis Plan for Study J4E-MC-IMMB is based on the protocol dated 13MAR2023.

Table 1.1. SAP Version History Summary

SAP Version	Approval Date	Change	Rationale
1	See date on Page 1	Not Applicable	Original version

1. Introduction

The purpose of this Statistical Analysis Plan (SAP) is to describe and specify the analyses relevant across the different intervention specific appendices (ISAs) of the atopic dermatitis master protocol (ADMP). The ADMP-specific SAP (MP-SAP) will specify

1. baseline characteristics of interest
2. safety analyses common across ISAs
 - a. overall safety including the posttreatment follow-up period, which accounts for safety events after dosing stops but drug has not washed out, and
 - b. safety during the induction treatment period, which is common to all ISAs, and
3. analysis framework for borrowing placebo data in the ADMP.

There are no changes to the analyses described in Protocol J4E-MC-IMMB (IMMB).

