4.6. Safety Analyses

For safety analyses, p-values will not be included unless specified in the ISA-SAP.

Table 4.1. Baseline and Postbaseline Period Definitions for Overall and Induction Safety Analyses

Analysis Type	Baseline Period	Postbaseline Period
TEAEs (induction safety analyses)	Starts from informed consent date for IMMB to just prior to the time of first dose.	Starts at the time of first dose of the study intervention and ends at the earliest of the following: 
 • Time of discontinuation from ISA • Time of discontinuation from study drug • Time of completing induction treatment period (time of the first dose in the maintenance treatment period, if relevant, or the date of the last visit in the induction treatment period), or • Database cut-off date for ongoing studies
TEAEs (overall safety analyses)	
Randomized in the initial period: Starts from informed consent date for IMMB to just prior to the time of first dose.
 
Assigned to Escape Arm from Placebo (if applicable): From the informed consent date for IMMB to just prior to the time of first dose of active study intervention on the escape arm.
	
For participants randomized to active study intervention in the initial period or assigned to escape arm from placebo: Starts at the time of first dose of the active study intervention and ends at the earliest of the following: 
 • Time of discontinuation from ISA • Time of ISA completion, or • Database cut-off date for ongoing studies 
 
For participants initially randomized to placebo: Starts at the time of first dose and ends at the earliest of the following: 
 • Time of discontinuation from ISA • Time of ISA completion • Time of first dose on the escape arm (if applicable), or • Database cut-off date for ongoing studies 

Analysis Type	Baseline Period	Postbaseline Period

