The planned summaries for AEs are provided in [Table 4.2](#)**Error! Reference source not found..**

Table 4.2. Tables and Listings Related to Adverse Events

Analysis	Details	Analyses
Overview of AEs	The number and percent of participants with: 
 • At least 1 TEAE • SAE • death, and • permanent discontinuation from study intervention due to an AE. 	Overall and Induction Analyses
TEAEs by PT within SOC	The number of participants, percent of participants, and IR of TEAEs using MedDRA PT nested within SOC. SOCs will be ordered by the difference in IRs between all LY and placebo.	Overall and Induction Analyses
Maximum Severity TEAEs by PT	
The number and percent of participants with TEAEs by maximum severity using MedDRA PT.
 
For each participant and TEAE, the maximum severity for the MedDRA PT is the maximum postbaseline severity observed from all associated LLTs mapping to the MedDRA PT.
 
The maximum severity will be determined based on the nonmissing severities. If all severities are missing for the defined postbaseline period of interest, it will show as missing in the table.
 
Events will be ordered by risk difference (total LY versus placebo) within SOC.
 
SOCS will be listed by risk difference.
	Induction Analysis
TEAEs occurring at $\geq 5\%$ by PT	The number of participants, percent of participants, and IR of TEAEs using MedDRA PT occurring in $\geq 5\%$ before rounding. Events will be ordered by decreasing difference in IRs.	Induction Analysis
Listing of AEs leading to permanent discontinuation of study intervention	Primary AE listed on the disposition form will be used and planned treatment group will be listed.	--
Listing of AEs leading to permanent discontinuation from study	Primary AE listed on the disposition form will be used and planned treatment group will be listed.	--
Listing of SAEs	SAEs resulting in death will be identified through a flag in the listing and planned treatment group will be listed.	--

Abbreviations: AE = adverse event; IR = incidence rate; LLT = Lowest Level Term; LY = Lilly product number; MedDRA = Medical Dictionary for Drug Regulatory Activities; PT = Preferred Term; SAE = serious adverse event; SOC = System Organ Class; TEAE = treatment-emergent adverse event.

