 1. Complicated: documented ocular (cornea or deeper structure; for example, iritis, keratitis, retinitis, and so on) or motor nerve development.
 2. Uncomplicated: multidermatomal cases.
 - iii. Disseminated: systemic infection, visceral, or widespread cutaneous (for example, 5 or more dermatomes or from 3 to 4 dermatomes including at least 1 noncontiguous [nonadjacent]).
 - c. TE, active tuberculosis infection is an OI.

Table 4.6 describes the planned summary tables related to infection safety.

Table 4.6. Summary Tables, Figures, and Listings Related to Infection Safety

Analysis	Details	Sample
Summary of TE Infections	The number and percent of participants with ≥ 1 TE infection, serious infection (death or SAE), temporary or permanent discontinuation of study intervention due to infection, TE OI, and TE infections of interest.	Induction and Overall Analyses
TE Infections – Infections of Interest	The number of participants, percent of participants, and IRs for participants with ≥ 1 TE infection of interest, maximum severity, serious infection (death or SAE), temporary or permanent discontinuation of study intervention, and whether the event is ongoing or resolved. TE infections of interest: upper respiratory infection, herpes zoster, other herpes infections, conjunctivitis, and candida.	Induction Analysis
Listing of Serious Infections	Includes participant identification, treatment group, SOC/PT, event start date, severity, action taken, relationship to study treatment or non-study treatment, and whether the SAE caused discontinuation.	--
Listing of TE OIs	Includes participant identification, treatment group, SOC/PT, event start date, severity, action taken, relationship to study treatment or non-study treatment, and whether the SAE caused discontinuation.	--

Abbreviations: TE = treatment-emergent; OI = opportunistic infection; IR = incidence rate; SOC = System Organ Class; PT = Preferred Term; SAE = serious adverse event.

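### Grouped incidence rates, maximum severity and resolution status for the SAP's infections of interest are planned for induction only; the overall analysis gives these groups crude percentages over unequal follow-up

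*SAP*

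**What the plan says.** The SAP supplied is the master-protocol SAP. Its Introduction promises two safety views: one of induction, and one of "overall safety including the posttreatment follow-up period".

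Table 4.6 (SAP 4.6.5.4) splits the infection outputs as follows.

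- The detailed row covers "TE infections of interest: upper respiratory infection, herpes zoster, other herpes infections, conjunctivitis, and candida". It reports number, percent, incidence rate (IR), maximum severity, seriousness, discontinuation, and whether the event is ongoing or resolved. Its sample is the Induction Analysis.
- The summary row reports "The number and percent of participants with ≥ 1 TE infection, serious infection (death or SAE" and goes on to discontinuation due to infection, opportunistic infections (OIs) and the infections of interest. Its sample is both Induction and Overall, but it has no IR.
- The listings of serious infections and of OIs carry no period limit. Each shows "event start date, severity, action taken, relationship to study treatment or non-study treatment, and whether the SAE caused discontinuation".

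Table 4.2 adds, for both analyses, "The number of participants, percent of participants, and IR of TEAEs using MedDRA PT nested within SOC". Its table of maximum severity by preferred term is for induction only.

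Under Table 4.1 the induction window for adverse events closes no later than "Time of completing induction treatment period". Protocol 4.1 describes a "double-blind, placebo-controlled, 16-week induction period". In the overall analysis, a placebo participant's window closes at the first escape dose, and an LY participant's window runs to ISA completion. The overall-safety estimand in SAP 4.4 takes as its population-level summary the difference in IRs for the adverse events of interest.

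Protocol 2.3.1 mentions infection under risk mitigation: the entry criteria "exclude potential participants who may be at greater risk of developing infections".

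**The concern.** The SAP singles out five infection groups and then gives their fullest description to the shorter of its two windows. Three things are missing from the overall analysis: an IR for each group as a group, maximum severity across all cases, and resolution status.

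The missing IR matters most, because number and percent cannot replace it here. Most placebo participants may stop contributing at Week 16, while LY participants contribute to the end of the study. Percentages over such different follow-up can show an LY excess when the true rates are equal. The SAP already defines person-years at risk (4.6.2) and the overall windows (Table 4.1), so the means to avoid this are in place but not applied to this row.

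IRs by single preferred term do not fill the gap. Participants with different herpes or candida terms are not combined into the SAP's own categories. On severity and outcome, localized herpes zoster is not an OI under SAP 4.6.5.4, even with ocular or motor-nerve involvement. A severe but nonserious case at Week 30 would be counted overall and would get an IR under its own term, but its severity and resolution would appear in no planned summary.

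**Working it through.** **Inputs from the documents**
- LY arms 96 + 68 + 28 = 192; placebo 68 (Protocol 4.1). The sum, 192 + 68 = 260, matches the total in Protocol 9.5.
- Induction lasts 16 weeks. The last dose is at Week 40 (Protocol Table 2) and the last follow-up visit is about 12 weeks later (Protocol 4.1): 40 + 12 = Week 52.
- Time after escape from placebo counts as LY, and LY responders rerandomized to placebo still count as LY (SAP 4.4).

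**Assumptions**
- Escape fraction: the escape threshold is redacted. As a proxy I use 88%, the complement of the 12% placebo EASI-75 rate in Protocol 9.5, with a range of 0–100%. Escape is placed at Week 16.
- Dropout is not given. I use 0–30% during induction and 0–40% afterwards, with uniform stopping times, with and without the 12-week follow-up.
- One year is 52.1775 weeks. Censoring at first event is ignored in the person-time totals.

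**Step 1. LY-attributed person-time, no dropout**
- Induction: 192 × 16 / 52.1775 = 58.9 person-years.
- Weeks 16 to 52, randomized to LY: 192 × 36 / 52.1775 = 132.5.
- Escaped placebo at 88%: 68 × 0.88 × 36 / 52.1775 = 41.3.

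| Placebo escape | Total LY person-years | Share after induction |
|---|---|---|
| 0% | 191.3 | 69.2% |
| 50% | 214.8 | 72.6% |
| 88% | 232.6 | 74.7% |
| 100% | 238.3 | 75.3% |

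The lowest value in the dropout range has 30% and 40% dropout, no escape, and no follow-up after stopping:
- Induction: 192 × (0.3 × 8 + 0.7 × 16) = 2,611 weeks = 50.0 person-years.
- After induction: 192 × 0.7 × (0.4 × 12 + 0.6 × 36) = 3,548 weeks = 68.0 person-years.
- Share: 68.0 / 118.0 = 57.6%.

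The range is therefore about 58–75%. Counting only to the last dose at Week 40, with no dropout or escape, the share is 24/40 = 60%.

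**Step 2. What crude percentages do over unequal follow-up**

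Assume the same true rate in both groups, 10 per 100 person-years, with no dropout. The chance of a first event in w weeks is 1 − exp(−0.10 × w / 52.1775): 3.0% for 16 weeks, 6.7% for 36 weeks and 9.5% for 52 weeks.

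With 88% escape (59.8 of 68):
- LY: (192 × 9.5% + 59.8 × 6.7%) / 251.8 = 8.8%.
- Placebo: 0.88 × 3.0% + 0.12 × 9.5% = 3.8%.
- Ratio: 2.3, although the true rate ratio is 1.0.

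The ratio of percentages is 1.0 with no escape and 2.9 with full escape. An IR over person-years at risk would show 10 per 100 in both groups.

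**Step 3. What the overall row would add, and its limit**
- If a group had no LY events, the approximate 95% upper bound (3 / person-years) is 3 / 58.9 = 5.1 per 100 person-years from induction, and 3 / 232.6 = 1.3 from the overall analysis at 88% escape.
- The placebo comparator after Week 16 is thin. At 88% escape, 68 × 0.12 = 8.2 participants contribute 8.2 × 36 / 52.1775 = 5.6 person-years, against 132.5 + 41.3 = 173.8 for LY.

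**The case against.** The strongest objection is that this is the master SAP, which sets a common minimum. It leaves other safety analyses to the ISA-SAP, whose Section 4.6.5 may clarify or add to these. The escape arm and rerandomization are features of FR01, and the FR01 ISA-SAP is not available. This stands as a limit: the gap is shown for this SAP, not for the whole analysis plan.

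A second objection is that the induction focus is reasoned. SAP 4.4 calls induction the most direct and clean comparison across ISAs, and after Week 16 the randomized comparison breaks down. This justifies keeping the induction table as the main placebo comparison. It does not explain leaving out the overall one, since the adjacent summary row runs both.

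A reader might infer that seriousness and all infection IRs are confined to induction, or that the trial's statement on infection would rest on the first 16 of 52 weeks. The documents do not support either. Serious infections, discontinuations due to infection and OIs are counted overall. Serious infections and OIs are listed without a period limit, with severity. Single-term IRs are given overall. Narratives (SAP 4.6.3) run to the end of participation and cover serious events, permanent discontinuations due to adverse events and other events judged clinically important. A severe nonserious case could be described there if it met one of those criteria.

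A reader might also take the 69% as drug exposure. It is attributed time: it includes the 12 weeks after the last dose and time on placebo after rerandomization. Escape nonresponders are also to be discontinued from study intervention, so full follow-up is optimistic; hence the 58–75% range.

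Finally, infection is mentioned in the protocol as a reason for exclusions. The readable text of Protocol 2.3.1 expects no risk needing more than typical monitoring for such antibodies, and its list of antibody risks is redacted. The point does not need infection to be a prominent signal, only that the SAP itself selected these groups.

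**Conclusion.** The point holds in a narrow form and is minor. In this SAP, grouped IRs, maximum severity across all cases and resolution status for the infections of interest are planned for induction only. The overall number and percent are not comparable between groups, because follow-up differs by design, and they do not give the difference in IRs named by the overall-safety estimand. That estimand's endpoint also allows number and percent, and the SAP does not list which events are of interest. I read the groups in Table 4.6, which carry the same label, as included.

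The period without these summaries holds about 58–75% of LY-attributed person-time: 69% with no dropout and no escape, 75% with 88% escape. The 2.3-fold apparent excess is an illustration. It depends on the assumed rate of 10 per 100 person-years, the 88% escape proxy and no dropout, and it disappears if nobody escapes. Whether the FR01 ISA-SAP already closes the gap cannot be determined from these documents.

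**What to change.** In SAP Table 4.6, change the sample for the infections-of-interest row from Induction to Induction and Overall, using the adverse-event windows in Table 4.1 and the person-years at risk in 4.6.2. If the sponsor does not want to bind every ISA, make the same addition in Section 4.6.5 of the FR01 ISA-SAP, unless it is already there.

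Keep the induction table as the main placebo comparison. Add a note to the overall table that the placebo comparator after Week 16 is small and non-randomized, and that LY-attributed time includes posttreatment follow-up and time after rerandomization to placebo.

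The cost is one table cell, one footnote and one more output. It uses adverse-event and infection follow-up data already collected, so there is no added burden on participants. The main downside is that the overall contrast could be over-read, which the note addresses.

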4.6.5.5 Malignancy

A listing of TE malignancies regardless of type (that is, including non-melanoma skin cancers) will be reported.

4.7. Other Analyses

Section 4.7.1 describes subgroup analyses, while Section 4.7 of the ISA-SAP will specify additional analyses of interest.

4.7.1. Subgroup Analyses

Subgroup analyses will be performed on the primary endpoint/estimand(s) and may be performed on key secondary endpoints and/or estimands. The variables for subgroup analyses are specified in [Table 6.1](#).

4.8. Interim Analyses

Section 4.8 of the ISA-SAP will describe the interim analysis plan.

CCI

A large rectangular area of the page has been completely blacked out, obscuring several lines of text. The word 'CCI' is visible in the top-left corner of this redacted area.

